13.4 Randomization

After baseline assessments are complete, participants will be randomized with equal probability to the exercise intervention (N=49) or wait-list control (N=49). Randomization will be blocked on stage (stages II-IIIA vs. IIIB-IV) and body mass index (<30 kg/m² vs. \geq 30 kg/m²) and will use permuted blocks with random size.

13.5 Additional Efficacy Hypotheses, Outcome Measures, and Statistical Methods

Our exploratory analyses will investigate the effect of the moderate exercise intervention on 24-hour urinary norepinephrine levels. We will use the above GEE model in this investigation to compare the mean changes from baseline to 24-weeks between the exercise intervention and control groups. We will assess the relationships between the change from baseline to 24 weeks in each of the distress or quality of life measures and change from baseline to 24 weeks in each of the biomarkers (IL-6, VEGF, salivary cortisol, urinary norepinephrine) based on the Pearson correlation. Also, we will investigate the association between changes in the outcomes from baseline to 24 weeks (distress, Quality of Life, biomarkers) and exercise adherence among participants in the intervention group. We will provide the mean change in the outcome by category of exercise adherence (\geq 150 min/week, 120-149 min/week, 90-119 min/week, 60-89 min/week, 30-59 min/week, and <30 min/week).

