Exploratory Endpoints	
1. Urinary norepinephrine (biomarker of chronic stress) - mean change from baseline to 24 weeks between the exercise intervention and control group in mean 24-hour urine norepinephrine level.
 
2. Mean change in outcomes (distress, Quality of Life, biomarkers) by category of exercise adherence (Mean change in outcomes (distress, Quality of Life, biomarkers) by category of exercise adherence (Percent of participants who exercised: ≥150 minute per week (≥100% of goal), 120-149 minutes per week, (≥80% of goal), 90-119 minutes per week (≥60% to <80% of goal), 60-89 minutes per week (≥40% to <60% of goal), 30-59 minutes per week (≥20% to <40% of goal), <30 minutes per week (<20% of goal)).
 
3. Correlations of levels of distress or Quality of Life with changes in biomarkers

Type of control	Waitlist exercise intervention
Investigation Drug	N/A
Dose	N/A
Route of administration	N/A
Regimen	N/A
Trial Blinding	N/A
Treatment Groups	Home-based exercise intervention
Treatment Schedule	
The exercise prescription will consist of 150 minutes of moderate aerobic exercise (the equivalent of brisk walking or higher intensity) per week, with weekly telephone-based support by an exercise physiologist. The control group will maintain habitual levels of physical activity and will be offered the exercise intervention after 24 weeks.
 
Baseline and 24-week assessments will include validated questionnaires assessing distress and health-related quality of life, serum levels of IL-6 and VEGF, salivary cortisol levels measured at bedtime for three consecutive days, and 24-hour urinary norepinephrine levels. Participants will also complete questionnaires at 12 weeks to provide additional longitudinal data.
 
Adherence to the intervention will be assessed by daily activity logs, actigraphs, and completion of weekly telephone calls.

Efficacy Assessments	Less psychosocial distress, improved quality of life, decreased biomarkers of angiogenesis and chronic stress hypothesized in the exercise arm group.
Number of trial subjects	98
Estimated duration of trial	2 years
Duration of Participation	24 weeks

ABBREVIATIONS

Table of Contents

1.0	GENERAL INFORMATION	8

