3.1.2 Exploratory Objectives

1. To evaluate the effects of the moderate exercise intervention versus controls on 24-hour urinary norepinephrine levels (a biomarker of chronic stress).
2. To determine if improvements in levels of distress or Quality of Life correlate with changes in biomarkers.
3. To evaluate for a dose-response relationship between exercise and our outcomes of interest.

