3.3.2 Exploratory Endpoints

1. Urinary norepinephrine- mean change from baseline to 24 weeks between the exercise intervention and control group in mean 24-hour urine norepinephrine level.
2. Mean change in outcomes (distress, Quality of Life, biomarkers) by category of exercise adherence (Percent of participants who exercised: ≥ 150 minute per week ($\geq 100\%$ of goal), 120-149 minutes per week, ($\geq 80\%$ of goal), 90-119 minutes per week ($\geq 60\%$ to $< 80\%$ of goal), 60-89 minutes per week ($\geq 40\%$ to $< 60\%$ of goal), 30-59 minutes per week ($\geq 20\%$ to $< 40\%$ of goal), < 30 minutes per week ($< 20\%$ of goal).
3. Correlations of levels of distress or Quality of Life with changes in biomarkers

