13.3 Sample Size and Power

98 individuals will be randomized. Accounting for up to 20% drop-out, power calculations are based on 78 participants.

Table 1. Minimum detectable absolute difference in mean change from baseline to 24 weeks between two groups (n=39 for Control group and n=39 for Exercise group) for the study endpoints, given an intra-individual correlation (ρ) of 0.5, 0.65 or 0.8, at 80% power, and adjusting for the number of hypotheses tests with 7 primary endpoints (type I error of 0.05/7).

Endpoint	Mean	SD	Minimum detectable absolute difference (% change)		
			$\rho = 0.5$	$\rho = 0.65$	$\rho = 0.8$
Distress (Perceived Stress Scale) ^a	19.23	6.77	5.41 (28.16%)	4.53 (23.56%)	3.42 (17.81%)
Distress (Hospital Anxiety and Depression Scale-anxiety subscale) ^b	7.4	3.9	3.12 (42.15%)	2.61 (35.27%)	1.97 (26.66%)
Distress (Hospital Anxiety and Depression Scale-depression subscale) ^b	5.8	3.5	2.87 (48.26%)	2.346 (40.4%)	1.77 (30.52%)
Quality of Life (36-item Short Form Survey- Physical Component Score) ^c	45.6	9.2	7.36 (16.14%)	6.16 (13.5%)	4.65 (10.21%)
IL-6 (pg/mL) ^d	2	0.7	0.56 (27.99%)	0.47(23.42%)	0.35 (17.70%)
VEGF (pg/mL) ^e	192	158.2	126.5 (65.88%)	105.8 (55.12%)	80(41.67%)
Salivary cortisol (nmol/L) ^d	4	0.6	0.48 (12.0%)	0.4 (10.04%)	0.3 (7.59%)

Mean and SD obtained from: ^a Perceived Stress Scale score in ovarian cancer survivors at the end of primary chemotherapy (111), ^b Hospital Anxiety and Depression Scale anxiety and depression subscale scores in ovarian cancer survivors towards end of primary chemotherapy (112), ^c 36-item Short Form Survey- Physical Component Score in our randomized controlled trial of exercise in ovarian cancer survivors (17), ^d biomarker levels in ovarian cancer survivors 6 months after primary treatment(113), and ^e VEGF levels in ovarian cancer survivors after completion of primary chemotherapy (114).

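### The planned correlations between distress or quality-of-life change and biomarker change have no term for arm, so an exercise effect on both outcomes can look like a link between them

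*Combined protocol and SAP*

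**What the plan says.** Exploratory objective 2 (section 3.1.2) is "To determine if improvements in levels of distress or Quality of Life correlate with changes in biomarkers". The matching endpoint in section 3.3.2 reads "Correlations of levels of distress or Quality of Life with changes in biomarkers". Section 13.5 makes this operational. Change from baseline to 24 weeks in each distress or quality-of-life measure is related to "change from baseline to 24 weeks in each of the biomarkers (IL-6, VEGF, salivary cortisol, urinary norepinephrine"), and the assessment is "based on the Pearson correlation".

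Section 13.5 names no adjustment for arm, no arm-specific correlation and no restriction to one arm. Its next analysis is restricted: it concerns "exercise adherence among participants in the intervention group". Sections 13.2, 13.6 and 13.7 add no arm term to the correlations.

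The synopsis, under efficacy assessments, states the expected effects: "Less psychosocial distress, improved quality of life, decreased biomarkers of angiogenesis and chronic stress hypothesized in the exercise arm group". Section 13.2 sets a general rule that outcomes with asymmetric distributions are log-transformed.

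**The concern.** A correlation computed across two randomised arms has two sources. One is the association between the two changes among people in the same arm. The other is the shift of both arm means. If exercise lowers distress and also lowers a biomarker, the exercise arm lies towards one corner of the scatterplot and the control arm towards the other, so a slope appears even if the two changes are independent inside each arm.

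This analysis serves the biobehavioural pathway described in section 2.1, and it is the only planned analysis that links distress or quality-of-life changes to biomarker changes. Without an arm term it cannot separate two statements: that exercise moved both outcomes, and that people whose distress improved more also had larger biomarker changes. The randomised comparisons already address the first; objective 2 adds information only through the second.

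The induced sign also agrees with the hypothesis. It is positive for distress against biomarkers, where both are expected to fall, and negative for quality of life against biomarkers, where one is expected to rise and the other to fall. The artefact therefore favours the expected story, and it grows with the size of the trial's effects.

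**Working it through.** **Inputs.** Allocation is 1:1 (section 13.4: "participants will be randomized with equal probability to the exercise intervention (N=49) or wait-list control (N=49")). The analysable number is 78 (section 13.3: "n=39 for Control group and n=39 for Exercise group"). Table 1 uses a type I error of 0.05/7, 80% power and intra-individual correlations ρ of 0.5, 0.65 and 0.8. The documents give no figure for the correlation analysis, so effect sizes are taken as a range and anchored where possible.

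**Step 1: reproduce Table 1 and express it in SD of change.** SD of change = SD × √(2(1 − ρ)). Detectable difference = (z for two-sided 0.05/7 + z for 80% power) × SD of change × √(2/39).

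- (2.690 + 0.842) × √(2/39) = 3.532 × 0.2265 = 0.80 SD of change.
- Perceived Stress Scale, ρ = 0.5: SD of change = 6.77 × √1 = 6.77. Unrounded, the formula gives 5.415; Table 1 states 5.41.
- IL-6, ρ = 0.5: 0.80 × 0.7 = 0.56; Table 1 states 0.56.
- SF-36 physical component, ρ = 0.5: 0.80 × 9.2 = 7.36; Table 1 states 7.36.

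The table therefore corresponds to an effect of about 0.80 SD of change.

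**Step 2: a reported effect for comparison.** Section 2.3 gives SF-36 physical component changes of 1.8 ± 1.1 and −2.0 ± 1.2 (P = 0.02) in an earlier exercise trial of 144 ovarian cancer survivors. The difference is 3.8. Dividing by Table 1's SD of change:

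- ρ = 0.5: 3.8/9.2 = 0.41
- ρ = 0.65: 3.8/7.70 = 0.49
- ρ = 0.8: 3.8/5.82 = 0.65

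As a check, reading the ± values as standard errors gives 3.8/√(1.1² + 1.2²) = 3.8/1.63 = 2.33, which matches P = 0.02. With 72 per arm (assumed from 144), the SD of change is 1.63/√(2/72) = 9.8, and the effect is 3.8/9.8 = 0.39 SD.

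**Step 3: the induced correlation.** Let exercise shift the two changes by d₁ and d₂, in within-arm SDs, with zero correlation inside each arm. With equal arms the covariance of the combined sample is d₁d₂/4 and the variances are 1 + d₁²/4 and 1 + d₂²/4. Hence

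r = (d₁d₂/4) / √[(1 + d₁²/4)(1 + d₂²/4)].

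- 0.4 SD on both: 0.04/1.04 = 0.04
- 0.5 SD on both: 0.0625/1.0625 = 0.06
- 0.8 SD on both: 0.16/1.16 = 0.14

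**Step 4: how often a nominal two-sided 5% test rejects.** These rates come from 100,000 simulated trials per row, with normal data, 39 per arm and zero within-arm correlation.

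| Effect on the two changes (SD) | Induced r | Rejection, no arm term |
|---|---|---|
| 0.8 and 0 | 0.00 | 5% |
| 0.4 and 0.4 | 0.04 | 6% |
| 0.5 and 0.5 | 0.06 | 8% |
| 0.65 and 0.65 | 0.10 | 13% |
| 0.8 and 0.8 | 0.14 | 23% |

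With the arm-adjusted partial correlation, mean r is 0.00 and rejection about 5% in every row.

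The 5% critical value of r for 78 people is 0.22. An induced r of 0.14 therefore raises the false-positive rate and does not by itself guarantee a significant result.

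**The case against.** Five arguments go the other way.

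- **Combining the arms is inferred.** Section 13.5 never says so. If correlations within each arm were intended, the artefact does not arise. This stands as a caveat, but the adjacent restriction of the adherence analysis makes the combined reading the natural one, and the text should settle it.
- **0.8 SD is a detectable effect, not an expected one.** This stands. The one arm effect the documents report for a primary outcome is about 0.4 SD on most readings. If both outcomes moved by that amount, the inflation would be slight (6%). Quoting only the top of the range would mislead, and the documents give no support for effects above 0.8 SD.
- **The unadjusted correlation answers the objective as worded.** Literally it does. It is a legitimate description, but it cannot carry the pathway interpretation. That is a reason to show it beside the adjusted one.
- **Scale.** A reader might infer that Pearson correlation on untransformed change conflicts with the planned logging of skewed biomarkers. The documents do not support that: section 13.2's rule covers outcome variables generally, and 13.5 does not say that it is set aside.
- **Number of correlations.** A reader might also fold the multiplicity of many pairs into this point. That is a separate matter: section 13.5 sets no significance rule for these correlations and labels the analyses exploratory.

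**Conclusion.** The point holds as a limited one about an exploratory analysis. As naturally read, section 13.5 yields a correlation that mixes the arm effect with the within-arm association. With no within-arm link, the false-positive rate at nominal 5% runs from about 6% (0.4 SD on both changes) through 8% (0.5 SD) to about 23% (0.8 SD).

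This rests on both arms being combined, 78 participants with both changes measured, normal data and an exercise effect on both outcomes. The artefact is zero if either outcome is unmoved. For norepinephrine the number will be below 78, because section 8.1 omits urine collection for participants who opt out of clinic visits.

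A reader might infer that the plan will manufacture a pathway finding, or that its main results are compromised. Neither follows. At the effect size seen in the earlier trial the distortion is small, and the primary comparisons, their type I error and the sample size are untouched. What is at risk is the mechanistic reading of exploratory objective 2, most of all if exercise has large effects on both outcomes.

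**What to change.** In section 13.5, state that the main analysis for exploratory objective 2 is the partial correlation of change with change, adjusted for randomised arm (or, equivalently in purpose, a regression of one change on the other with an arm term). Compute it on the scale chosen under section 13.2 and report it with a 95% confidence interval. The unadjusted correlation may be shown beside it, labelled as including any effect of arm.

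The cost is a sentence or two in the plan and one degree of freedom per correlation. No new data, visits or assays are needed, and no primary analysis changes.

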3.2 Study Population

Individuals with histologically or cytologically confirmed stage II-IV epithelial ovarian, peritoneal, or fallopian tube carcinoma (collectively referred to as ovarian cancer) who have completed primary surgery and chemotherapy within one to six months of screening, and are in clinical remission (no clinical evidence of disease on exam and normal CA-125 level) will be eligible. Individuals must be physically able to undertake a moderate exercise program. Individuals will be excluded if they have contraindications to initiating a training program (75), or if they already exercise >90 minutes per week of moderate intensity. Persons with peripheral neuropathy and lower extremity edema will not be excluded, but will be evaluated by their oncologist and the exercise physiologist for safety.

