5.2 Exclusion Criteria

5.2.1 Subjects who have had primary surgery, chemotherapy and/or radiation therapy within 4 weeks prior to screening. Subjects may have received other surgeries not performed for primary treatment (for example, removal of intraperitoneal port, laparoscopic cholecystectomy, etc.) within 1 month of screening as long as they do not have post-operative restrictions that would preclude participating in a moderate intensity exercise program once enrolled in the clinical trial.

5.2.2 Self-reported inability to walk at least 2 blocks (at any pace).

5.2.3 Prior brain metastasis is not an exclusion, as long as subject is in clinical remission.

5.2.4 Uncontrolled or concurrent illness including, but not limited to: unstable angina pectoris, recent (within six months) myocardial infarction, uncontrolled cardiac arrhythmia, uncontrolled congestive heart failure, hypertrophic obstructive cardiomyopathy, uncontrolled hypertension (systolic > 200, diastolic > 120), conditions (cardiovascular, respiratory, or musculoskeletal disease or joint problems) that preclude moderate physical activity. Subjects with a history of cardiac arrest, or those with moderate/severe aortic or mitral stenosis may be eligible if their treating physician determines that moderate physical activity is safe. Moderate arthritis that does not preclude physical activity is not a reason for ineligibility. Individuals with lymphedema or peripheral neuropathy will not be excluded. They will be evaluated by the exercise physiologist for safety and modifications to the exercise prescription will be made as appropriate.

5.2.5 Psychiatric illness/social situations that would limit compliance with study requirements.

5.2.6 Already physically active >90 minutes per week of moderate exercise.

[figure not shown]

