Questionnaires (Appendix D) – all questionnaires will be completed at baseline, 12, and 24 weeks, unless specifically noted. Questionnaires may be completed online through REDCap, or on paper. Paper questionnaires may be mailed with a provided self-addressed stamped envelope or brought to clinic if participant opts for clinic visits.

Protocol 10045

- **Demographics, health history, and habits** (Demographics and health history at baseline only): Information will be collected on demographics, medical history, and health habits including medication use, tobacco use, and use of complementary and alternative therapies via a questionnaire.
- **7-day Physical Activity Log:** Participants will complete a seven-day Physical Activity Log (for the preceding 7 days) at baseline (before randomization) and 24-week assessments. Physical Activity Logs of exercise during the seven days preceding the assessment point will be used to determine minutes per week of moderate physical activity.
- Assessment of physical activity prior to ovarian cancer diagnosis (baseline only): Questions 6-8 of Form 34 v2: Personal Habits Questionnaire used by the Women's Health Initiative (https://www.whi.org/researchers/studydoc_layouts/15/WopiFrame.aspx?sourcedoc=/researchers/studydoc/WHI%20Forms/F034%20v2.pdf&action=default) will be included to assess the participant's estimated level of physical activity in the 2 years prior to their diagnosis of ovarian cancer.
- **Perceived Stress Scale (82):** This instrument uses a Likert-type rating scale to measure the degree to which situations in life are perceived as stressful, specifically unpredictable, uncontrollable, and overloading. The scale has excellent psychometric properties and relates to relevant outcomes in expected ways. Internal consistency is high with Chronbach's alpha's ranging from 0.75 to 0.86.
- **Hospital Anxiety and Depression Scale, anxiety and depression (HADS-A and HADS-D) subscales (83, 84):** This instrument is a well validated and widely used assessment of anxiety and depression. The 14-item scale has two subscales, anxiety and depression, derived from 7 questions each. Participant responses are scored on a scale of 0 to 3 with variable anchors (85). The Internal reliability is high with Chronbach's alpha for the anxiety scale ranging from 0.89-0.93 and 0.86-0.90 for the depression scale (83, 84).

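### The exercise dose-response analysis in section 13.5 does not account for the 0 to 90 min/week that participants may already do at entry

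*Combined protocol and SAP*

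**What the plan says.** Section 3.1.2 gives the third exploratory objective as "To evaluate for a dose-response relationship between exercise and our outcomes of interest". Section 13.5 serves it by examining "the association between changes in the outcomes from baseline to 24 weeks" against "exercise adherence among participants in the intervention group", and then specifies: "We will provide the mean change in the outcome by category of exercise adherence". The six bands are total minutes per week: 150 or more, 120-149, 90-119, 60-89, 30-59 and under 30. The synopsis and section 3.3.2 express the same bands as percentages of a 150-minute goal.

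Exclusion 5.2.6 reads "Already physically active >90 minutes per week of moderate exercise", and section 3.2 excludes people on the same limit: "or if they already exercise >90 minutes per week of moderate intensity". Activity at entry may therefore lie anywhere from 0 to 90 min/week.

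Baseline activity is measured. Section 8.1 states: "Participants will complete a seven-day Physical Activity Log (for the preceding 7 days) at baseline (before randomization) and 24-week assessments". The study calendar in Appendix C also puts the activity monitor at weeks 0 and 24 in both arms. Section 8.1 says that actigraphy will allow a preliminary look at dose-response, but defines no exposure for it. Section 13.2 gives age and BMI as example covariates; baseline activity is not named there or in 13.5.

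**The concern.** The response in this analysis is a change from baseline, while the exposure is a level that includes whatever the participant was doing before she joined. Elsewhere in section 13.5, change is paired with change, when distress and quality of life are correlated with biomarkers. Only the exercise analysis lacks a baseline term on one side.

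Two things follow if the bands are read as dose. Participants with very different amounts of added exercise share a band, which blurs any gradient. Entry activity may also differ between bands, and it may be related to the baseline outcome: section 2.1 cites two observational studies linking physical activity with better quality of life in ovarian cancer survivors. A gradient across bands could then partly reflect who was active at entry. At stake is the interpretation of one exploratory objective.

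**Working it through.** **1. The plan's own percentages.** Cut-point / 150 gives 150/150 = 100%, 120/150 = 80%, 90/150 = 60%, 60/150 = 40% and 30/150 = 20%. These match the synopsis and section 3.3.2, so the bands are attained total minutes over a fixed goal with no baseline term.

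**2. Minutes added that each band can contain.** Minutes added = attained - baseline, with baseline between 0 and 90 (section 5.2.6). The lower bound is the band's lower limit minus 90; the upper bound is its upper limit minus 0.

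| Attained min/week | Possible minutes added |
|---|---|
| under 30 | -90 to 29 |
| 30-59 | -60 to 59 |
| 60-89 | -30 to 89 |
| 90-119 | 0 to 119 |
| 120-149 | 30 to 149 |
| 150 or more | 60 upward |

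All neighbouring bands overlap.

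**3. Individual cases.**
- Enters at 90, stays at 90: 90/150 = 60% of goal, with 90 - 90 = 0 added.
- Attains exactly 150: added minutes run from 150 - 90 = 60 to 150 - 0 = 150, a ratio of 2.5.
- Enters at 90 and attains 120: 30 added. Enters at 0 and attains 90: 90 added, yet she sits one band lower.

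**4. Typical size.** In the earlier ovarian cancer exercise trial described in section 2.3, mean baseline was 31 min/week and mean attained activity in the intervention arm was 166. That gives 166 - 31 = 135 added; 31/166 = 19% of attained minutes pre-existed.

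**5. Band means.** The documents give neither this trial's baseline distribution nor its correlation with attained minutes, so both are assumed. Attained minutes are taken as normal with mean 169.0 and SD 49.2, which reproduces the earlier trial's 65% at 150 or more and 84% at 120 or more. Baseline is a scaled beta on 0-90 with mean 31. The arm has n = 39, as in Table 1 of section 13.3, with 1,500 simulated arms per correlation.

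| Correlation, baseline with attained | Mean baseline: 90-119 band / top band | Mean minutes added, lowest to highest band | Discordant pairs | Chance of at least one inversion |
|---|---|---|---|---|
| -0.5 | 46.4 / 23.9 | -51.4, -13.8, 23.4, 60.6, 97.7, 173.3 | 5.0% | 12% |
| 0 | 30.4 / 30.8 | -13.7, 17.7, 47.4, 76.5, 105.0, 166.2 | 7.6% | 22% |
| 0.3 | 22.1 / 35.1 | 6.7, 33.5, 59.7, 84.7, 110.1, 162.0 | 8.4% | 16% |
| 0.6 | 13.4 / 39.0 | 13.9, 43.4, 69.5, 93.8, 115.5, 157.9 | 8.0% | 7% |
| 0.9 | 5.0 / 43.0 | 18.3, 47.7, 76.2, 101.9, 123.5, 153.8 | 4.3% | 0.1% |

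A discordant pair is two participants in different bands whose minutes added run against the band order. An inversion is a pair of neighbouring non-empty bands whose observed mean minutes added are out of order. For that, the bands' mean baselines must differ by more than their attained means, about 30 minutes for adjacent closed bands. Expected minutes added rise across bands in every scenario. The lower bands are sparse: 16% of 39 is about 6 participants below 120 min/week, spread over four bands. Except at zero correlation, entry activity differs between bands, and the sign of that difference follows the sign of the correlation.

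**6. Does subtracting baseline help in a regression?** Let A be attained minutes, B baseline minutes and Y0 the baseline outcome. Then b(A - B) + cB + dY0 = bA + (c - b)B + dY0. The coefficient b is the same either way: once B is in a linear model, redefining exposure as minutes added changes nothing.

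**The case against.** The strongest reply is that section 13.5 describes adherence. The prescription in section 7.2 is a total of 150 minutes, so attained minutes over 150 is the right measure of how far it was followed. That stands, and the bands should stay. It does not settle the matter, because no other analysis is specified for the dose-response objective, and the actigraphy remark in section 8.1 leaves the exposure undefined.

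A reader might infer that the bands will put the dose in the wrong order. The documents do not support that. Individual pairs can be reversed, but the plan reports band means, and expected minutes added keep their order in every scenario tried. The earlier trial also had 84% of its intervention arm at 120 min/week or more, so participants who stay at their entry level may be few.

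A reader might also infer that someone whose activity is unchanged should show no change in outcome. That cannot be assumed: participants are one to six months past primary treatment, and the earlier trial's control arm lost 2.0 points on the SF-36 physical component score. Whether the level of activity or the increase drives change is open.

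Finally, subtracting the baseline log from the daily log would mix instruments. The baseline log in Appendix D asks for recalled exercise vigorous enough to cause sweating; the daily log in Appendix E records bouts of at least 10 minutes with a perceived-exertion rating. This objection stands and shapes the fix.

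**Conclusion.** The point holds in a limited form. Section 13.5 leaves entry activity of up to 60% of the goal (90/150) out of the only analysis it specifies for the dose-response objective. The bounds in steps 2 and 3 follow from the documents alone, provided that the baseline log agrees with the 90-minute limit applied at screening. The likely harm is blurring and confounding by entry activity, of unknown direction. Under the assumed distributions, about 4% to 8% of between-band pairs are discordant, and the chance of at least one inversion of neighbouring band means is 0.1% to 22%, depending on the assumed correlation. The analysis is exploratory, confined to one arm and has no decision rule. The randomised primary comparison is unaffected. This is a cheap improvement, not a defect in the main result.

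**What to change.** In section 13.5:

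- Keep the percent-of-goal bands, described as a summary of adherence.
- For the third exploratory objective, add a linear regression in the exercise arm of outcome change on attained min/week as a continuous variable, adjusted for baseline min/week and the baseline value of the outcome.
- If minutes added are also reported, take them from one instrument at both times: the 7-day log at baseline and 24 weeks, or the actigraph at weeks 0 and 24. Do not subtract the baseline recall log from the daily log.
- Label the result exploratory and non-randomised, since attained minutes are not assigned by randomisation.

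The cost is SAP wording and a little extra analysis. Both covariates are already collected before randomisation. The downside is two covariates fitted with about 39 participants, so estimates will be imprecise.
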